#### **4.5.13.2 Approval by the Institutional Review Board or Ethics Committee**

Collection, storage, and analysis of RBR samples is contingent upon the review and approval of the exploratory research and the RBR portion of the Informed Consent Form by each site's IRB/EC and, if applicable, an appropriate regulatory body. If a site has not been granted approval for RBR sampling, this section of the protocol (Section 4.5.13) will not be applicable at that site.

#### **4.5.13.3 Sample Collection**

The following samples will be stored in the RBR and used for research purposes, including, but not limited to, research on biomarkers related to ipatasertib, rucaparib, the HR and *PI3K* pathway, immune infiltration/activation, apoptosis, and the biology of breast, ovarian, and prostate cancer, or drug safety:

- **Left over blood, serum, plasma, and tumor tissue samples** (with the exception of remaining archival tissue blocks, which will be returned to sites) and any derivatives thereof (e.g., DNA, RNA, proteins, peptides)

The above samples may be sent to one or more laboratories for analysis of germline or somatic mutations via WGS, whole exome sequencing (WES), or other genomic analysis methods. Genomics is increasingly informing researcher's understanding of disease pathobiology. WGS and WES provide a comprehensive characterization of the genome and exome, respectively, and, along with clinical data collected in this study, may increase the opportunity for developing new therapeutic approaches or new methods for monitoring efficacy and safety or predicting which patients are more likely to respond to a drug or develop adverse events.

Data generated from RBR samples will be analyzed in the context of this study but will also be explored in aggregate with data from other studies. The availability of a larger dataset will assist in identification and characterization of important biomarkers and pathways to support future drug development.

For sampling procedures, storage conditions, and shipment instructions, see the laboratory manual.

RBR samples are to be stored until they are no longer needed or until they are exhausted. However, the RBR storage period will be in accordance with the IRB/EC-approved Informed Consent Form and applicable laws (e.g., health authority requirements).

#### **4.5.13.4 Confidentiality**

RBR samples and associated data will be labeled with a unique patient identification number.

Patient medical information associated with RBR samples is confidential and may be disclosed to third parties only as permitted by the Informed Consent Form (or separate authorization for use and disclosure of personal health information) signed by the patient, unless permitted or required by law.

Given the complexity and exploratory nature of the analyses of RBR samples, data derived from these analyses will generally not be provided to study investigators or patients unless required by law. The aggregate results of any conducted research will be available in accordance with the effective Sponsor policy on study data publication.

Data generated from RBR samples must be available for inspection upon request by representatives of national and local health authorities, and Sponsor monitors, representatives, and collaborators, as appropriate.

Any inventions and resulting patents, improvements, and/or know-how originating from the use of the RBR data will become and remain the exclusive and unburdened property of the Sponsor, except where agreed otherwise.

#### **4.5.13.5 Consent to Participate in the Research Biosample Repository**

The Informed Consent Form will contain a separate section that addresses participation in the RBR. The investigator or authorized designee will explain to each patient the objectives, methods, and potential hazards of participation in the RBR. Patients will be told that they are free to refuse to participate and may withdraw their consent at any time and for any reason during the storage period. A separate, specific signature will be required to document a patient's agreement to provide optional RBR samples. Patients who decline to participate will not provide a separate signature.

The investigator should document whether or not the patient has given consent to participate and (if applicable) the date(s) of consent, by completing the RBR Research Sample Informed Consent eCRF.

In the event of an RBR patient's death or loss of competence, the patient's samples and data will continue to be used as part of the RBR research.

#### **4.5.13.6 Withdrawal from the Research Biosample Repository**

Patients who give consent to provide RBR samples have the right to withdraw their consent at any time for any reason. However, if RBR samples have been tested prior to withdrawal of consent, results from those tests will remain as part of the overall research data. If a patient wishes to withdraw consent to the testing of his or her RBR samples during the study, the investigator must inform the Medical Monitor in writing of the patient's wishes through use of the appropriate RBR Subject Withdrawal Form and must enter the date of withdrawal on the RBR Research Sample Withdrawal of Informed Consent eCRF. If a patient wishes to withdraw consent to the testing of his or her RBR

samples after closure of the site, the investigator must inform the Sponsor by emailing the study number and patient number to the following email address:

global\[contact]

A patient's withdrawal from this study does not, by itself, constitute withdrawal of consent for testing of RBR samples. Likewise, a patient's withdrawal of consent for testing of RBR samples does not constitute withdrawal from this study.

#### **4.5.13.7 Monitoring and Oversight**

RBR samples will be tracked in a manner consistent with Good Clinical Practice by a quality-controlled, auditable, and appropriately validated laboratory information management system, to ensure compliance with data confidentiality as well as adherence to authorized use of samples as specified in this protocol and in the Informed Consent Form. Sponsor monitors and auditors will have direct access to appropriate parts of records relating to patient participation in the RBR for the purposes of verifying the data provided to the Sponsor. The site will permit monitoring, audits, IRB/EC review, and health authority inspections by providing direct access to source data and documents related to the RBR samples.

### **4.6 TREATMENT, PATIENT, STUDY, AND SITE DISCONTINUATION**

#### **4.6.1 Study Treatment Discontinuation**

Patients must permanently discontinue study treatment if they experience any of the following:

- Any medical condition that the investigator or Sponsor determines may jeopardize the patient's safety if he or she continues to receive study treatment
- Unacceptable toxicity related to study treatment (see Section 5)
- Investigator or Sponsor determination that treatment discontinuation is in the best interest of the patient
- Pregnancy
- Use of another non-protocol-specified anti-cancer therapy
- Disease progression per investigator assessment according to RECIST v1.1 or PCWG3
  - Rise in CA-125 or rise in PSA without radiographic disease progression does not require treatment discontinuation

The primary reason for study treatment discontinuation should be documented on the appropriate eCRF. Patients who discontinue study treatment prematurely will not be replaced, with the exception of patients enrolled in Part 1 (Dose-Escalation Phase) who are not considered DLT-evaluable (see Section 3.1.2).

Patients will return to the clinic for a treatment discontinuation visit  $\leq 30$  days after the final dose of study drug (see Appendix 1 for additional details).

After treatment discontinuation, information on survival follow-up and new anti-cancer therapy will be collected via telephone calls, patient medical records, and/or clinic visits approximately every 3 months until death (unless the patient withdraws consent or the Sponsor terminates the study). Patients with prostate cancer who discontinue prior to radiographic progression should continue tumor assessments until radiographically assessed disease progression.

#### **4.6.2 Patient Discontinuation from Study**

Patients have the right to voluntarily withdraw from the study at any time for any reason. In addition, the investigator has the right to withdraw a patient from the study at any time. Reasons for withdrawal from the study may include, but are not limited to, the following:

- Patient withdrawal of consent
- Study termination or site closure
- Investigator or Sponsor determines it is in the best interest of the patient
- Patient non-compliance, defined as failure to comply with protocol requirements as determined by the investigator or Sponsor

Every effort should be made to obtain information on patients who withdraw from the study but have not withdrawn consent. The primary reason for withdrawal from the study should be documented on the appropriate eCRF. If a patient requests to be withdrawn from the study, this request must be documented in the source documents and signed by the investigator. Patients who withdraw from the study will not be replaced except for patients in Part 1 who are not considered DLT-evaluable (see Section 3.1.2).

If a patient withdraws from the study, the study staff may use a public information source (e.g., county records) to obtain information about survival status.

#### **4.6.3 Study Discontinuation**

The Sponsor has the right to terminate this study at any time. Reasons for terminating the study may include, but are not limited to, the following:

- The incidence or severity of adverse events in this or other studies indicates a potential health hazard to patients
- Patient enrollment is unsatisfactory

The Sponsor will notify the investigator if the Sponsor decides to discontinue the study.

#### **4.6.4 Site Discontinuation**

The Sponsor has the right to close a site at any time. Reasons for closing a site may include, but are not limited to, the following:

- Excessively slow recruitment
- Poor protocol adherence

- Inaccurate or incomplete data recording
- Non-compliance with the International Council for Harmonisation (ICH) guideline for Good Clinical Practice
- No study activity (i.e., all patients have completed the study and all obligations have been fulfilled)

## **5. ASSESSMENT OF SAFETY**

### **5.1 SAFETY PLAN**

The safety plan for patients in this study is based on clinical experience with ipatasertib and rucaparib in completed and ongoing studies. The anticipated important safety risks are outlined below (see Section 5.1.1 and Section 5.1.2). Ipatasertib is not approved, and clinical development is ongoing. Refer to the Ipatasertib Investigator's Brochure for a complete summary of safety information. Refer to the Rucaparib Investigator's Brochure for a complete summary of safety information.

Several measures will be taken to ensure the safety of patients participating in this study. Eligibility criteria have been designed to exclude patients at higher risk for toxicities. Patients will undergo safety monitoring during the study, including assessment of the nature, frequency, and severity of adverse events. In addition, guidelines for managing adverse events, including criteria for dosage modification and treatment interruption or discontinuation, are provided below.

#### **5.1.1 Risks Associated with Ipatasertib**

Ipatasertib has been associated with risks such as the following: nausea, vomiting, diarrhea, stomatitis/mucosal inflammation, asthenia/fatigue, hyperglycemia, erythema multiforme, and rash.

Refer to the Ipatasertib Investigator's Brochure for a detailed description of the anticipated safety risks for Ipatasertib.

#### **5.1.2 Risks Associated with Rucaparib**

Rucaparib has been associated with risks such as the following: anemia, thrombocytopenia, *febrile neutropenia*, nausea, constipation, vomiting, diarrhea, asthenia/fatigue, *pyrexia*, *increased blood creatinine*, *decreased neutrophil count*, and *dyspnea*.

*Note: AST or ALT elevation is not considered an identified risk in the Rucaparib Investigator's Brochure but has been reported with rucaparib.*

Refer to the Rucaparib Investigator's Brochure for a detailed description of the anticipated safety risks for Rucaparib.

### **5.1.3 Risks Associated with Ipatasertib and Rucaparib**

Ipatasertib and rucaparib have both been associated with *the following* risks: nausea, vomiting, diarrhea, *and* asthenia/fatigue.

*Note: AST or ALT elevation is a potential risk in the Ipatasertib Investigator's Brochure. AST or ALT elevation is not considered as a potential or identified risk in the Rucaparib Investigator's Brochure but has been reported with rucaparib.*

Refer to the Ipatasertib and Rucaparib Investigator's Brochure for a detailed description of the anticipated safety risks for rucaparib.

### **5.1.4 Management of Patients Who Experience Adverse Events**

Guidelines for managing selected adverse events are provided in this section to improve safety and tolerability; however, patients may be treated per institutional practices as appropriate. If any observed toxicity is attributable to only one drug as assessed by the investigator, the dose of the other drug may not require modification. The reasons for dose modifications (e.g., interruptions, reduction, and withdrawal) or delays, supportive measure taken, and the outcome will be recorded in the eCRF.

#### **5.1.4.1 General Management of Rucaparib-Related Adverse Events**

Treatment with rucaparib should be held if any of the following are observed:

- Grade 3 or 4 hematologic toxicity
- Grade 3 or 4 non-hematologic toxicity (except for alopecia, nausea, vomiting, diarrhea adequately controlled with systemic antiemetic/antidiarrheal medication administered in standard doses according to the study center routines, and Grade 3 ALT/AST elevations not accompanied by bilirubin > ULN or other signs of liver dysfunction)
- In addition, at the discretion of the investigator, the dose of rucaparib may be held and/or reduced for Grade 2 toxicity that is attributed to rucaparib and not adequately controlled by concomitant medications and/or supportive care.

Rucaparib should be held until the toxicity resolves to Grade  $\leq 2$ . BID dosing may then be resumed at either the same dose or a lower dose per investigator discretion. If treatment is resumed at the same dose and the patient soon experiences the same toxicity, the dose should be reduced following resolution of the repeated event to Grade  $\leq 2$ . If the patient continues to experience the same toxicity, additional dose reduction steps are permitted down to a minimum dose of 300 mg BID (see [Table 11](#)).

Unless otherwise specified, rucaparib dose re-escalation upon resolution of toxicity to Grade  $\leq 1$  is permitted upon agreement between the investigator and Sponsor.

If a patient continues to experience the same toxicity despite multiple dose reduction steps to the lowest allowed dose or if dosing with rucaparib is interrupted for

>28 consecutive days due to the toxicity, treatment should be discontinued unless otherwise agreed between the investigator and the Sponsor.

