### **3.1.2 Definition of Dose-Limiting Toxicity**

A DLT will be defined as any of the following adverse events related to study treatments occurring during the DLT reporting period, which corresponds to the first cycle of study treatment (i.e., from Cycle 1, Day –7 to Day 28; Cycle 1 has 35 days):

- Any death related to study treatment
- Grade 4 neutropenia lasting for  $\geq 7$  days
- Grade  $\geq 3$  neutropenia complicated by fever  $\geq 38^{\circ}\text{C}$  or infection
- Grade 4 thrombocytopenia lasting for  $\geq 7$  days
- Grade  $\geq 3$  thrombocytopenia complicated by hemorrhage or that requires transfusion
- Study treatment-related Grade  $\geq 3$  non-hematologic toxicity (graded according to the NCI CTCAE, v5.0) except for the following:
  - Grade 3 fatigue, asthenia, fever, anorexia, or constipation
  - Grade 3 nausea, vomiting, or diarrhea that responds to maximal supportive care within 72 hours
  - Grade 3 rash that resolves to Grade 1 within 7 days with maximal supportive care
  - Grade 3 hyperglycemia that is controlled with subcutaneous insulin
  - *Grade 3 ALT or AST elevation that is not accompanied by a concurrent increase in bilirubin (i.e., greater than the upper limit of normal [ULN])*
  - *Any other Grade 3 laboratory abnormality that is asymptomatic and is deemed not to be clinically significant by the investigator*

Patients who miss seven or more doses of either ipatasertib or rucaparib during the DLT-evaluation period for reasons other than a DLT will be replaced. In addition, patients who are discontinued from the study prior to completing the DLT-evaluation period for reasons other than a DLT (e.g., disease progression, consent withdrawn) will also be replaced. If a patient experiences a DLT, study treatment will be interrupted immediately for that individual and a safety assessment will be conducted.

The NCI CTCAE v5.0 will be used to characterize the toxicity profile of the study treatments for all patients.

An interim analysis for safety (including DLTs) will be performed by the Sponsor prior to the Dose-Expansion Phase (Part 2) to assess data from all patients in the Dose-Escalation Phase (Part 1). The interim analysis will be completed after the last evaluable patient in Part 1 has completed the first cycle of treatment. The combination dose levels demonstrating acceptable safety will be carried forward to the Dose-Expansion Phase (Part 2) of the study.

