#### **5.1.4.2 Management of Rucaparib Treatment-Emergent Creatinine Elevations**

Rucaparib is a potent inhibitor of MATE1 and MATE2-K transporters, which are involved in active secretion of creatinine. Rucaparib-mediated creatinine elevation occurs early in treatment and then stabilizes. Creatinine elevation is not typically accompanied by elevations in urea (BUN). Creatinine elevation resolves with *treatment interruption* of rucaparib and recurs with re-challenge. Creatinine elevation has not been associated with evidence or reports of permanent renal impairment. The following are guidelines for rucaparib dose modifications in the events of Grade  $\geq 3$  creatinine elevations:

- For Grade 4 isolated creatinine elevations (BUN  $\leq$  ULN), hold rucaparib and investigate with ultrasound, urinalysis, and so on for potential alternative etiologies. When other reversible causes are treated or ruled out and the event has resolved to Grade 1 or better, then resume rucaparib at a reduced dose.
- For Grade 3 isolated creatinine elevations (BUN  $\leq$  ULN), investigate with ultrasound, urinalysis, and so on for potential alternative etiologies. In the absence of another reversible cause (e.g., obstructions or infections) or evidence of renal injury, continue rucaparib at the same dose. Hold rucaparib for other reversible causes until the patient is treated and the event has resolved to Grade 1 or better, and then resume rucaparib at the same dose.

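### Sections 5.1.4.1 and 5.1.4.2 give opposite rucaparib instructions for isolated Grade 3 creatinine elevation without another cause, and no text says which section governs

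*Combined protocol and SAP*

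**What the plan says.** Section 5.1.4.1 (general management of rucaparib-related events) opens with "Treatment with rucaparib should be held if any of the following are observed". One trigger is "Grade 3 or 4 non-hematologic toxicity (except for alopecia, nausea, vomiting, diarrhea adequately controlled with systemic antiemetic/antidiarrheal medication". The same bracket then adds Grade 3 ALT/AST elevation without raised bilirubin or other liver dysfunction. Creatinine is not mentioned. The hold lasts until Grade 2 or less, after which "BID dosing may then be resumed at either the same dose or a lower dose per investigator discretion".

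Section 5.1.4.2 (creatinine) treats isolated elevations, meaning BUN at or below ULN, in three branches:

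- Grade 3, no other cause: "In the absence of another reversible cause (e.g., obstructions or infections) or evidence of renal injury, continue rucaparib at the same dose".
- Grade 3, another cause: "Hold rucaparib for other reversible causes until the patient is treated and the event has resolved to Grade 1 or better", followed by restart at the same dose.
- Grade 4: hold, then restart at Grade 1 or better at a reduced dose.

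For Part 1, section 3.1.2 exempts from DLT status a Grade 3 laboratory abnormality that causes no symptoms and that the investigator judges not clinically significant. It also states: "Patients who miss seven or more doses of either ipatasertib or rucaparib during the DLT-evaluation period for reasons other than a DLT will be replaced". Section 5.1.4.9 and Table 13 use a different evaluability test, based on receipt of about 70% of the planned dose in Cycle 1.

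**The concern.** A site with an isolated Grade 3 creatinine rise and no other explanation finds one section telling it to hold rucaparib and the next telling it to carry on. The exceptions in 5.1.4.1 include events that have their own later sections (diarrhea, nausea and vomiting, liver enzymes), so leaving out creatinine can be read as deliberate. The only deferring phrase in 5.1.4.1 concerns dose re-escalation. The event is also foreseeable: section 5.1.2 lists increased creatinine as a rucaparib risk, and 5.1.4.2 says the rise comes early and returns on re-challenge.

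Two things are at stake. Rucaparib exposure could depend on which section a site follows, in both parts. In Part 1, the choice could also decide whether a patient remains in the DLT fraction from which the RP2D is chosen.

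**Working it through.** **1. The instructions side by side**

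| Isolated creatinine event | 5.1.4.1 | 5.1.4.2 |
|---|---|---|
| Grade 3, no other reversible cause, no renal injury | Hold; restart at Grade 2 or less, same or lower dose | Continue, same dose |
| Grade 3, other reversible cause | Hold; restart as above | Hold; restart at Grade 1 or better, same dose |
| Grade 4 | Hold; restart as above | Hold; restart at Grade 1 or better, reduced dose |

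Only the first row is a direct opposition. In the other two, a site that follows 5.1.4.2 also satisfies the permissive restart in 5.1.4.1. A site that restarts at Grade 2 under 5.1.4.1 does not satisfy 5.1.4.2.

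**2. When a hold leads to replacement in Part 1**

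The plan's own figures reproduce: 4 dose levels × 6 patients = 24, and the DLT window is 7 + 28 = 35 days. Rucaparib starts on the evening of Cycle 1 Day 1 (section 4.3.2.2), so planned Cycle 1 doses are 1 + 27 × 2 = 55. Seven doses at two per day is 3.5 days.

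For an event that is not a DLT:

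- Up to 6 doses missed (3 days): the patient stays in and counts as a non-DLT.
- 7 to 16 missed (48/55 = 87.3% down to 39/55 = 70.9% received): replaced under 3.1.2, but still evaluable under the 70% rule.
- 17 or more missed (38/55 = 69.1% received, or less): not evaluable under either rule.

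Appendix 1 schedules chemistry on Cycle 1 Days 8 and 15. A hold from Day 8 until the Day 15 result would miss about 7 × 2 = 14 doses (41/55 = 74.5% received). A hold past seven doses is therefore plausible, though an unscheduled test could shorten it.

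**3. Effect on the RP2D verdict if the patient is replaced**

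The criterion is a DLT fraction below one-third with at least 6 patients (section 3.1.1.1): 1/6 passes and 2/6 does not. Let p be the true DLT probability, which is an assumption.

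- Patient counted as a non-DLT: P(pass) = (1−p)^5 + 5p(1−p)^4.
- Patient replaced: P(pass) = (1−p)^6 + 6p(1−p)^5.
- Difference: 5p²(1−p)^4. This is exactly one DLT among the other five and a DLT in the replacement.

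| p | Counted | Replaced | Difference |
|---|---|---|---|
| 0.10 | 0.919 | 0.886 | 0.033 |
| 0.20 | 0.737 | 0.655 | 0.082 |
| 0.30 | 0.528 | 0.420 | 0.108 |

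The difference peaks at p = 1/3, at 0.110, and is 0.104 at p = 0.40.

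**4. How often this could arise**

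The documents give no Grade 3 creatinine rate. At assumed rates r of 2%, 5% and 10%, the chance of at least one such patient among six is 1 − (1−r)^6 = 11.4%, 26.5% and 46.9%. Multiplying these in order by the three differences above gives roughly 0.4%, 2% and 5% per level. Those products assume that 5.1.4.1 is always followed, that every hold reaches seven doses, and that the 70% rule never keeps the patient in.

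**The case against.** The best defence is that 5.1.4.1 is headed as general and 5.1.4.2 is specific to creatinine, so the specific section governs. The protocol works this way elsewhere: the diarrhea and rash tables restart rucaparib at Grade 1 or better, not at the general Grade 2. Section 5.1.4 also calls all of this guidance and allows institutional practice. This makes the likely intent clearer, but it does not settle the text. No sentence sets precedence, and 5.1.4.1 names exceptions for other events with their own sections. Latitude for local practice makes variation between sites more likely, not less.

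Several stronger readings are tempting, and the documents do not support them:

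- A reader might infer that the two sections are opposed throughout. They are opposed in one branch only.
- A reader might infer that the same Part 1 patient is necessarily replaced under one section and counted under the other. That requires a non-DLT judgement and at least seven missed doses. If the event is symptomatic or judged clinically significant, a related Grade 3 rise is a DLT under either section.
- A reader might infer that Grade 3 events are expected inside the DLT window. Section 5.1.4.2 says that creatinine elevation comes early; it does not say so of Grade 3 elevation, and it gives no time frame.
- A reader might picture repeated holds ending in dose reduction during Part 1 Cycle 1. Section 5.1.4.9 and Table 13 bar reductions then, except for a DLT or by Sponsor decision.

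**Conclusion.** The contradiction stands in the current text for isolated Grade 3 creatinine elevation with no other reversible cause and no renal injury. In the remaining branches only the restart criteria differ. The firm consequence is that rucaparib exposure can differ by site in both parts; the documents do not allow its size to be estimated.

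The RP2D consequence is conditional and small: about 3 to 11 percentage points for an affected level, given replacement and assumed true DLT rates of 10% to 30%. It is lower once the chance of the event is included. Between 7 and 16 missed doses it also rests on the unresolved difference between the seven-dose rule and the 70% rule, which is a separate matter. This is a wording conflict worth correcting, not evidence that the dose-finding design is unsound. Which clinical instruction is right is not judged here.

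**What to change.** Reconcile the two sections. State in 5.1.4.1 which section governs isolated creatinine elevation, so that one hold rule and one restart rule (grade and dose) apply. The sponsor's clinical team decides which. This takes a sentence at the next amendment and needs no new data or patients.

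Do not add a sentence to 3.1.2 keeping every patient with a creatinine hold in the DLT denominator. A patient who missed 17 or more of 55 doses would then count as DLT-free with less than 70% of planned rucaparib, against 5.1.4.9 and Table 13, and levels would be tilted toward passing.
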